Neutrophil Extracellular Trap Formation in Newborn Infants at Risk for Inflammatory Syndromes

Protocol v 1, 1/15/2019

PI: [name]

IRB# 119244

Background

Dysregulation of acute inflammation contributes to the pathogenesis of many neonatal and pediatric diseases including sepsis, acute respiratory distress syndrome (ARDS), neonatal chronic lung disease (nCLD), retinopathy of prematurity (ROP), and necrotizing enterocolitis (NEC).

nCLD causes significant morbidity and mortality in the United States. nCLD is a complication of preterm birth that results from prolonged mechanical ventilation required for chronic respiratory failure. It occurs in 30 - 50% of mechanically ventilated extremely low birthweight infants (ELBW) with respiratory distress. While surfactant therapy and pre- or postnatal steroids have decreased the severity of nCLD, this significant morbidity associated with preterm birth remains common in at – risk infants, with about 8,000 to 10,000 new cases occurring annually in the US. The mortality rate due to nCLD in ELBW infants remains high from 15 - 40%. Furthermore, nCLD remains the most common cause of long-term hospitalization in neonates and is also associated with developmental delay. Whether or not dysregulated NET formation contributes to the pathogenesis of nCLD remains unknown.

ROP is the most common cause of pediatric blindness. Dysregulated inflammation is also implicated in the pathogenesis of ROP leading to retinal detachment and blindness. To date, no one has determined whether dysregulated NET formation contributes to ROP.

NEC, predominantly a disease of premature infants, afflicts $\approx 5 - 10\%$ of very low birth weight infants (< 1500 grams), develops typically in the 3rd to 4th week of life and often results in mortality. Infants born closer to term rarely develop NEC but those that do typically exhibit other risk factors such as ductal-dependent congenital heart disease or mesenteric ischemia. For these patients, NEC occurs typically in the first week of life and can prove fatal. Other sequelae of NEC include intestinal perforation, short gut syndrome, prolonged total parenteral nutrition with possible concomitant liver failure and a prolonged intensive care unit stay. While the etiology remains unknown, risk factors of prematurity, enteral feeds, infection and intestinal ischemia predict an increased risk for NEC⁵.

The final common pathogenic pathway for NEC appears to depend on a dysregulated, pro-inflammatory response to bacterial translocation across an immature or damaged gastrointestinal epithelial barrier. Animal and human studies of NEC pathogenesis implicate inflammatory cytokines and phospholipids such as tumor necrosis factor alpha, Interleukin-8 and platelet activating factor (PAF). One animal model also demonstrated that aortic lipopolysaccharide (LPS) infusion caused a NEC-like syndrome in rats ⁶. Each of these biologically active inflammatory mediators activates the polymorphonuclear leukocyte (PMN)⁷, the primary effector cell of the acute inflammatory response to tissue injury or infection.

Data from animal models suggest a prominent role of the PMN in the pathogenesis of NEC. Musemeche et al. induced NEC-like disease in rats by intra-aortic injection of PAF⁸. They then used vinblastine, a chemotherapeutic agent, to induce neutropenia in rats four days prior to intra-aortic injection of PAF. The vinblastine-induced neutropenia protected against the clinical and pathologic manifestations of NEC-like disease.

The role of the human PMN in the acute inflammatory response is well documented. PMNs play a fundamental role in the innate immune response and are rapidly recruited to areas of injury or inflammation where they participate in bacterial phagocytosis and killing. Disorders associated with a deficiency or impairment of PMN function (neutropenia, chronic granulomatous disease (CGD), leukocyte adhesion deficiency) predispose to infections with gram-negative and gram-positive bacteria⁹. However, regulation of this potent component of the acute inflammatory response is imperative. Disorders such as ARDS, ischemia/reperfusion injury, and rheumatoid arthritis appear to result from the dysregulation of the PMNs' acute inflammatory response.

Recently, neutrophils isolated from healthy adult donors were shown to undergo programmed cell death distinct from apoptosis and necrosis to form neutrophil extracellular traps (NETs). NETs are extensive lattices of extracellular DNA and chromatin decorated with anti-microbial proteins and degradative enzymes such as myeloperoxidase and neutrophil elastase (NE). NETs effect extracellular killing of bacteria and fungi. Our laboratory recently characterized impaired NET formation as a novel innate immune deficiency of human newborn infants and showed that PMNs isolated from the cord blood of newborn infants, both term and preterm, demonstrated impaired NET formation and extracellular bacterial killing as compared to PMNs isolated from healthy adults. However, the timing for developmental maturation of newborn infant PMN NET formation remains unknown. Furthermore, while failure of NET formation contributes to the predisposition for and severity of bacterial and fungal infections associated with disorders such as CGD, dysregulated and inappropriately robust NET formation may lead to immune-mediated host tissue damage such as autoimmune small vessel vasculitis.

Using data generated from the previous version of this IRB application (IRB_00039621 – Neutrophil Extracellular Trap Formation in Newborn Infants at Risk for Necrotizing Enterocolitis – Closed on 11/8/2018), we recently discovered a new regulatory mechanism governing NET formation in the first 2 weeks following birth for neonates, whether term or preterm. Using cord blood samples as well as samples of peripheral blood taken serially from neonates over the first 2 months of life, we recently identified a family of NET-Inhibitory Peptides (NIPs) which circulate in the fetus and neonate and potently inhibit PMNs from forming NETs. These NIPs inhibit NET formation despite stimulation with many NET-generating agonists like LPS, PMA, live gram+ or gram- bacteria, heme, or viruses. We further examined the use of these NIPs in the setting of in vivo sepsis. We found that pretreatment with the NIPs increased survival in the cecal ligation and puncture model of polymicrobial sepsis by 40-60%, with the survival advantage most likely due to decreased NET-mediated inflammatory tissue damage. With these published results (Yost CC, et al., JCI 2016), we are now funded by the NIH to evaluate the use of NIPs as therapeutic agents in preclinical models of neonatal sepsis. These studies will determine regulatory pathways governing NIP expression in the fetus and newborn, NIP mechanism of action, and efficacy in neonatal sepsis.

We hypothesize that NET formation contributes to the pathogenesis of inflammatory syndromes associated with sequelae of prematurity including sepsis, nCLD, ROP, and NEC by inappropriately releasing degradative proteins and tissue destructive enzymes into the inflammatory milieu of the premature infant. We further hypothesize that NIPs may provide protection against NET-associated inflammatory tissue damage.

Study Purposes and Objectives:

The following study is best described as a prospective, in vitro longitudinal cellular biology study of LPS/PAFstimulated PMNs isolated from the cord and peripheral blood of premature infants at risk for inflammatory sequelae associated with prematurity (including neonatal Chronic Lung Disease (nCLD), early and late onset sepsis, necrotizing enterocolitis (NEC), and retinopathy of prematurity), and from term infants not considered at risk for such sequelae. In the specific case of NEC, we will also assay for NET formation in gastrointestinal tissue samples obtained at the time of surgery for severe NEC in enrolled prematurely born infants if that occurs. Such tissue samples will not be collected for other inflammatory syndromes of prematurity.

These studies are the first of their kind and aim to answer important questions such as the impact of dysregulated NET formation in the pathogenesis of these inflammatory sequelae of prematurity, the regulatory mechanisms

governing NET formation in newborn infants, the role of our newly discovered NET-Inhibitory Peptides (NIPs) as endogenous regulators of NET formation, and their potential use as novel therapeutic agents for dysregulated NET formation.

Inclusion Criteria:

Eligible Patients

1. Preterm infant patients delivered at UUMC and hospitalized in the NICU who are \leq 1500 grams or < 30 weeks gestational age at birth

Cord blood sample obtained at delivery

Peripheral blood sample obtained during IV start under anesthesia at any elective surgeries during the first year of life

2. Term infants delivered at UUMC without complication, either via cesarean section or vaginal delivery.

Cord blood sample obtained at delivery

Heel-prick blood sample obtained at 24 hours of life

Exclusion criteria:

None

Study Procedures:

Recruitment: We will screen charts through a waiver of authorization for potential participants within the University of Utah covered entity. Eligible participants identified through the waiver of authorization will be identified once they are admitted to the hospital for clinical management, with the expectation of delivery during the current hospital admission.

Inclusion/exclusion criteria will be reviewed with the patient's chart and then approached once initial eligibility criteria have been verified.

Pregnant women admitted to labor and delivery and who meet the eligibility criteria for term deliveries without complication will be identified and approached about the study prior to delivery.

Pregnant women admitted to labor and delivery in an emergent manner and who meet the eligibility criteria for preterm delivery at <30 weeks gestational age may be approached prior to delivery, when deemed appropriate by the patient's care team.

Consent: For consent of healthy term neonates, all mothers will be approached after admission to the Labor and Delivery Unit at UUMC. Informed consent for their neonate's participation in our study will be sought by [name]. If the delivery is precipitous and cord blood is collected, the families of potential healthy term neonate participants may also be approached after the fact but within 24 hours after delivery if appropriate. It is anticipated that this will be the exception and not the rule. Furthermore, any umbilical cord blood collected will be used and tested for any clinical indications before being considered for use in research for this project. Also,

research related activities connected with this study will not begin until after consent has been obtained from the family of the newborn.

For consent of preterm neonates born at less than 30 weeks gestation, all mothers admitted to the Labor and Delivery Unit at UUMC and meeting inclusion criteria will be approached for consent prior to delivery by [name] or his research team. In each case, the obstetrical clinical care team will determine whether initiating the consent process prenatally is appropriate. The family's physical and emotional state prior to delivery will be considered in this determination. If appropriate, [name] or his research team will consent for study participation prenatally and proceed with use of the umbilical cord blood at that moment. If not deemed appropriate, [name] research team will collect the umbilical cord blood and approach the family for informed consent within 24 hours after delivery. Furthermore, any umbilical cord blood collected will be used and tested for any clinical indications before being considered for use in research for this project. Also, research related activities connected with this study will not begin until after consent has been obtained from the family of the newborn.

Phlebotomy:

Patient Group #1: Prematurely born infants in the UUMC and PCH NICUs

After delivery, cord blood will be drawn from the ligated umbilical cord and placenta. For premature deliveries of infants weighing less than 1500 grams, it is estimated that only 5 – 10 mL of cord blood will be obtained. The resuscitation and treatment of a premature infant often requires cord blood specimens for such clinical tests as arterial and venous cord blood gases and blood type and crossmatch in preparation for probable future blood transfusions. These specific clinical cord blood samples will be collected before study blood collection. The residual cord blood will be dripped into sterile 8 mL EDTA-anticoagulated vacutainers, labeled with a study generated patient identifier and transported by [name] or his laboratory technicians to his lab in the Eccles Institute of Genetics for immediate PMN isolation and sample stabilization. This rapid isolation and sample stabilization is necessary given the short life of PMNs *in vitro* and the potential for PMN activation after isolation.

The family will then be approached regarding informed consent as discussed below. If informed consent is obtained, preparations will be made to obtain 3 serial 0.5 ml samples of peripheral blood during the infant's NICU stay. Samples will be collected on the routine lab draw day that most closely correlates with the following days of life (DOL) #: 3, 7, and 14 if still in the NICU at either UUMC or PCH.

Longitudinal samples will be collected into a 0.5 ml EDTA-anticoagulated microtainers and processed in an identical manner to the cord blood already collected. These serial samples will only be collected during routine clinical laboratory draws occurring around the scheduled DOL. No new lines, IVs or heel stick wounds will be started or made for the sole purpose of drawing the scheduled study sample.

For the small subset of at-risk infants who develop NEC requiring surgery at PCH, whether born at UUMC or transported to PCH from a referring institution, we will also obtain fixed and paraffin-embedded gastrointestinal tissue samples at the time of surgery for analysis of NET formation. These samples will be obtained by the pediatric surgical team at the time of exploratory laparotomy and processed by the diagnostic pathology service at PCH. For those infants transported to PCH with surgical NEC from referring institutions, informed consent will be requested upon admission to PCH NICU. If informed consent is obtained, the samples would be processed and transferred by [name] to his laboratory for further analysis.

Patient Group #2: Healthy term infants born at UUMC

After delivery, cord blood will be drawn from the ligated umbilical cord and placenta. For term deliveries at UUMC, it is estimated that approximately 15 - 25 mL of cord blood can be routinely obtained without compromising needs for possible clinical studies such as infant blood-typing. Samples will be dripped into sterile 8

mL EDTA-anticoagulated vacutainers, labeled with a study generated patient identifier and transported by [name] or his laboratory technicians to his lab in the Eccles Institute of Human Genetics for immediate PMN isolation and sample stabilization. Again, this rapid isolation and sample stabilization is necessary given the short life of PMNs *in vitro* and the potential for PMN activation after isolation.

The family will then be approached regarding informed consent as discussed below. If informed consent is obtained, preparations will be made to obtain one additional 1 ml sample of peripheral blood during the infant's heel stick wounding for the 24-hour metabolic screening test performed on all infants before DOL #3 and before hospital discharge. The sample will be collected into 2 0.5 ml EDTA-anticoagulated microtainers and processed in an identical manner to the cord blood already collected. This additional sample will only be collected during the routine 24 – 48-hour metabolic screening laboratory draw. No new lines, IVs or heel stick wounds will be started or made for the sole purpose of drawing the scheduled study sample.

Experimental Procedures:

After parental consent is obtained, PMNs will be isolated via positive immunoselection against CD15 antigen expression as previously described. PMNs will be stimulated with PAF or LPS and analyzed for NET formation via live cell imaging, quantitative extracellular DNA content and quantitative neutrophil elastase activity. For NEC tissue samples, NET formation will be qualitatively assessed via immunohistochemistry. NET-Inhibitory Peptide concentrations in blood plasma will be assessed via quantitative Western blotting and/or HPLC/MS² assays.

Live Cell Imaging:

Isolated PMNs will be allowed to adhere to lysinated glass coverslips and stimulated with PAF [10 nM] or LPS [100 ng/ml] for 1 - 4-hour time points. Cell impermeable and cell permeable intercalating DNA dyes will be used to differentially stain NET-associated, extracellular DNA and intracellular nuclear DNA. Qualitative assessment of NET formation will be captured and recorded via confocal microscopy.

Quantitative extracellular DNA Content Assay:

Supernatants following PAF/LPS stimulation and confocal imaging will be treated with DNase (66 U/ml for 15 minutes) to break up NETs and gently removed and analyzed for total DNA content. Supernatant DNA concentrations will be quantified by incubating the samples with Sytox Orange (1mM) and comparing the values against a concentration curve constructed with varying concentrations of a known DNA standard using fluorimetry with filter settings of 530(excitation)/ 645(emission) (BioTek Synergy HT).

Quantitative Myeloperoxidase (MPO)-DNA ELISA:

NET-associated MPO activity will be determined at selected time points as described. Briefly, the incubation medium will be gently removed and replaced with medium containing DNase (66 U/ml) for 15 min. A capture antibody against MPO will be employed as part of a MPO-DNA ELISA to provide quantitative levels of NET formation. A detection antibody against human DNA will serve as the detection antibody.

Quantitative NIP Concentration in Human Plasma:

Plasma samples will be obtained from whole blood samples via centrifugation. The aliquots of the plasma will then be run on Tris-Tricine precast gels to resolve proteins and peptides with a molecular weight between 1 and 30 kD. A standard curve with increasing concentration of synthesized NIPs will be run on the same gel and concentration will be determined by comparing the fluorescent intensity of the plasma band to those of the standard curve. Alternatively, we are developing a HPLC/MS2 assay which will use a synthesized "heavy" variant of NIPs to quantify NIP concentration in plasma compared to a known amount of spiked "heavy" NIP.

Qualitative assessment of NET formation in NEC tissue specimens via immunohistochemistry:

NEC tissue specimens processed by pediatric pathology at PCMC and embedded in paraffin will be transported to [name] laboratory and analyzed for NET formation via immunofluorescence. Surgical samples will be sectioned at $5 - 10 \,\mu$ m thickness. NETs will be visualized by examining the colocalization of antibodies against DNA, histones, and neutrophil elastase.

Data Analysis:

NET formation as assessed qualitatively via live cell imaging and immunohistochemistry and quantitatively via extracellular DNA quantitation and neutrophil elastase activity assays.

We anticipate enrolling 40 prematurely born infants in patient group # 1, 20 healthy term newborn infants in patient group # 2 during this study.

Statistical comparisons for the quantitative assays of extracellular DNA and NE activity will be made via one-way ANOVA with post hoc Pairwise Multiple Comparisons made via the Holm-Sidak method.

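### Preterm infants are expected to be transfused, but the plan does not record transfusion or separate pre- from post-transfusion samples, so a postnatal change in NIP or NET values cannot be assigned to the infant's own biology

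*Combined protocol and SAP*

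**What the plan says.** **Expected exposure.** Under Phlebotomy, Patient Group #1, the clinical uses of preterm cord blood that take priority over the study include typing and "crossmatch in preparation for probable future blood transfusions". The Exclusion criteria are given as none.

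**Sampling.** After cord blood, three 0.5 ml samples are planned: "Samples will be collected on the routine lab draw day that most closely correlates with the following days of life (DOL) #: 3, 7, and 14", provided the infant is still in the NICU. The other condition is that "These serial samples will only be collected during routine clinical laboratory draws occurring around the scheduled DOL". Neither condition refers to transfusion.

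**Comparator.** Group #2 is "Term infants delivered at UUMC without complication, either via cesarean section or vaginal delivery". These infants give cord blood and one peripheral sample at the metabolic screen. The Phlebotomy text for this group mentions only collection "without compromising needs for possible clinical studies such as infant blood-typing".

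**Interpretation.** The Background describes NIPs as peptides "which circulate in the fetus and neonate and potently inhibit PMNs from forming NETs" and places the regulatory mechanism in the first two weeks after birth. Study Purposes and Objectives sets out to study NIPs as endogenous regulators. Experimental Procedures measures NIP concentration in plasma, and measures NET formation in PMNs that have been isolated and then stimulated.

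**Analysis.** Data Analysis gives a one-way ANOVA with Holm-Sidak comparisons for extracellular DNA and neutrophil elastase activity. It names no covariate and gives no analysis for NIP concentration.

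**The concern.** The study follows NIP and NET formation from cord blood through day 14 to learn how the newborn regulates NET formation. In preterm infants, transfusion falls in the same two weeks. A plasma concentration measured after transfusion belongs partly to the infant and partly to the donor. If donor plasma carries little NIP, measured NIP falls for a reason unrelated to maturation.

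The exposure is aligned with the study's time axis. Postnatal transfusion cannot have affected cord blood, and the share of infants ever transfused can only rise after that. It probably also rises with illness, and the hypothesis links NET formation to sepsis, nCLD, ROP and NEC. Both the age trend and any association with outcome could therefore carry a transfusion component. Since the plan collects nothing on transfusion, its analysis could neither detect nor bound that component.

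**Working it through.** The plan states no figure on this point to reproduce. It also gives no alpha, power, effect size or SD behind the 40 preterm and 20 term infants. The check is mainly textual, followed by illustrations on assumed inputs.

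**1. The passages side by side**

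| Link | Status |
|---|---|
| Preterm infants are likely to be transfused | Stated (Phlebotomy, Group #1) |
| Term infants are seldom transfused | Inferred from the uncomplicated-delivery criterion and the absence of any mention |
| Samples are taken without regard to transfusion | Follows from the only two stated conditions |
| NIP is read as endogenous | Stated (Study Purposes and Objectives) |
| Donor plasma is low in NIP | Not stated; no adult or donor level is given |
| Product, volume and transfusion rate | Not given |
| Transfusion recorded or handled in analysis | Absent throughout |

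**2. Dilution of plasma NIP (all inputs assumed)**

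Let donor plasma contain no NIP and have volume r relative to the infant's plasma volume. The fractional fall is r/(1+r).

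- r = 0.05, 0.10, 0.20, 0.30 gives 4.8%, 9.1%, 16.7%, 23.1%.
- For a plasma-containing product at an assumed 15 mL/kg into 45 to 55 mL/kg, the fall is 15/(15+55) = 21% to 15/(15+45) = 25%.
- Two such exposures give 1-(55/70)^2 = 38% to 1-(45/60)^2 = 44% if volume returns to baseline with proportional loss of peptide. If volume simply accumulates, they give 1-55/85 = 35% to 1-45/75 = 40%. If fluid is lost and peptide retained, the dilution reverses.
- Packed cells carry little plasma, so dilution would be smaller. New NIP production and clearance are ignored throughout.

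**3. Effect on the mean age change**

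If a share T of infants at a given age has had one exposure, each with fractional fall f, and starting NIP is unrelated to transfusion, the mean falls by T × f even with no maturation.

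- Low end: 0.25 × 4.8% = 1.2%.
- Middle: 0.5 × 21% = 10.5%.
- High end: 1 × 25% = 25%.

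In cord blood T = 0, so this fall would appear as an age effect.

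**4. Effect on one preterm-term comparison (40 against 20)**

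Assume two-sided alpha 0.05, no true difference, a within-group SD of 1, and transfused infants shifted by s SD. Then d = T × s and SE = sqrt[(1 + T(1-T)s²)/40 + 1/20]. For T = 0.5 and s = 0.5, d = 0.25 and SE = sqrt(1.0625/40 + 0.05) = 0.277. The chance of a nominally significant result is 0.147.

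| T | s = 0.25 | s = 0.5 | s = 1.0 |
|---|---|---|---|
| 0.25 | 0.056 | 0.074 | 0.144 |
| 0.5 | 0.074 | 0.147 | 0.419 |
| 0.75 | 0.105 | 0.274 | 0.757 |
| 1 | 0.150 | 0.447 | 0.955 |

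For scale, with the same alpha and 80% power this comparison detects (1.960 + 0.842) × sqrt(1/20 + 1/40) = 0.77 SD. The table runs from negligible to dominant, and nothing the plan collects would place the study within it.

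**The case against.** **The NET route is weak.** A reader might infer that transfused red cells supply heme and so drive the NET readout, because the Background lists "bacteria, heme, or viruses" among NET-generating stimuli. The documents do not support that step. They do not say transfusion supplies heme, and PMNs are isolated by CD15 selection before PAF or LPS is added. Heme would have to act in the infant beforehand and its effect survive isolation. This objection stands: for NET values the effect is possible but indirect.

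**Dilution is not established.** It is tempting to conclude that adult plasma must dilute NIP because NIPs are described in the fetus and neonate and adult PMNs form NETs. Behaviour of isolated adult cells says nothing about adult plasma, and no donor level is reported. This stands as well, so dilution remains conditional.

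**Restricting to untransfused samples can mislead.** Late untransfused samples come from fewer, probably healthier infants. A real maturational change could disappear there through selection or low power. This stands and limits what the restricted analysis can show.

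**The gap is broader, and charts can be searched later.** The plan lists no clinical covariates and specifies no NIP or age-profile analysis. Transfusion details would ordinarily be in the chart, so much could be recovered retrospectively. That is fair and makes the point more modest. However, the choice of which draw to use cannot be made in retrospect, and the analysis carries more weight if stated beforehand.

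**The later sample is a separate matter.** The inclusion item "Peripheral blood sample obtained during IV start under anesthesia at any elective surgeries during the first year of life" lies outside the day 3 to 14 window, and the point does not rest on it.

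**Conclusion.** The point holds as a gap in data capture and attribution. The plan expects transfusion in preterm infants, reads their later values as endogenous, and has no means of separating the two. Plasma NIP is directly exposed, on the assumption that donor NIP is low; the isolated-PMN assays are exposed only indirectly. Cord samples are not affected by postnatal transfusion.

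The size is unknown. The illustrations give a mean NIP fall of roughly 1% to 25% from single exposures, and a false-positive chance of 5.6% to 95.5% in one preterm-term comparison. They depend on assumed volumes, shares and shifts, and should not be read as estimates.

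A reader might go further and conclude that transfusion explains the postnatal NIP or NET pattern, or that the day 3 to 14 data are invalid. The documents support neither conclusion. They show only that the plan as written could not rule transfusion out. That makes this an inexpensive improvement worth adopting, not a fatal flaw.

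**What to change.** 1. For each preterm peripheral sample, abstract three items from the chart: whether any transfusion came before it, the product, and the time since the last one.
2. Where a routine draw already precedes a planned same-day transfusion, take the study sample from that draw. This leaves care unchanged and respects the rule against additional sticks.
3. State the NIP and NET age comparisons in Data Analysis. Report them for all samples and again for samples before first transfusion, or fit a model with transfusion as a time-varying covariate.
4. Fix the interpretation in advance. If the two sets of results differ, or too few late samples precede transfusion, report that maturation cannot be separated from transfusion. Do not take loss of the trend in the restricted set as proof of a transfusion effect.

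**Cost.** Three chart fields per sample and one additional analysis, with no extra blood or procedure. The restricted set will be smaller and probably healthier, so its intervals will be wider and it is open to selection. The report should say so.

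### Preterm serial samples may be drawn off DOL 3, 7 and 14, and the planned one-way ANOVA can use age only as a nominal group (minor)

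*Combined protocol and SAP*

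**What the plan says.** Under Phlebotomy, Patient Group #1, the protocol plans that "preparations will be made to obtain 3 serial 0.5 ml samples of peripheral blood during the infant's NICU stay". Timing follows a nearest-draw rule: "Samples will be collected on the routine lab draw day that most closely correlates with the following days of life" 3, 7 and 14. Two further sentences bear on timing. One is a soft limit: "These serial samples will only be collected during routine clinical laboratory draws occurring around the scheduled DOL". The other bars draws made for the study: "No new lines, IVs or heel stick wounds will be started or made for the sole purpose of drawing the scheduled study sample". No tolerance in days is given, and nothing says that the time of the draw is recorded or used.

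For term infants, by contrast, the Phlebotomy section gives the heel-stick sample an explicit 24 to 48 hour range.

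Data Analysis plans a one-way ANOVA with Holm-Sidak pairwise comparisons for extracellular DNA and neutrophil elastase activity. It does not name the grouping factor, does not mention age at sampling, and names no analysis for NIP concentration.

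On the biology, the Background reports "a new regulatory mechanism governing NET formation in the first 2 weeks following birth for neonates, whether term or preterm". It also says that "the timing for developmental maturation of newborn infant PMN NET formation remains unknown".

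**The concern.** The study describes itself as longitudinal, and the timing of maturation is one of its open questions, so postnatal age is the variable along which the preterm results will be read. Clinical care decides when a sample is drawn, and the nearest-draw rule attaches that sample to a nominal day. A one-way ANOVA compares categories. If the categories are nominal days, a value drawn several days away counts as if it came from the target day. The groups then overlap in age, and a real trend over the first two weeks looks flatter and noisier than it is. The information that would prevent this, the actual age at each draw, is not mentioned in the plan.

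**Working it through.** **Figure to reproduce.** There is none. The 40 preterm and 20 term infants are anticipated enrolments without a power calculation, and no timing tolerance is stated.

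**Inputs from the protocol.** Targets t = 3, 7 and 14; the nearest routine draw is used; there is no numeric window; no draw is made for the study alone.

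**Assumption (not in the documents).** Routine draws occur every k days, k = 1 to 7. The first is equally likely on any of DOL 1 to k. Ties are split equally.

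**Formula.** With the first draw on day p, draws fall on p, p + k, p + 2k and so on. The sample for day t is the draw that minimises |p + jk − t|, for j = 0, 1, 2 and so on.

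**Weekly draws in full** (k = 7, p = 1 to 7):
- nearest to DOL 3: 1, 2, 3, 4, 5, 6, 7; mean 28/7 = 4
- nearest to DOL 7: 8, 9, 10, 4, 5, 6, 7; mean 49/7 = 7
- nearest to DOL 14: 15, 16, 17, 11, 12, 13, 14; mean 98/7 = 14

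Three of seven schedules place the DOL 14 sample before day 14, one on it and three after it (43%, 14%, 43%). For p = 4, 5, 6 and 7 the same draw is nearest to both DOL 3 and DOL 7: 4/7 = 57%.

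**All intervals:**

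| Draw every | DOL 3 group | DOL 7 group | DOL 14 group | DOL 14 sample before / on / after day 14 | One draw nearest both DOL 3 and 7 (ties counted) |
|---|---|---|---|---|---|
| 1 day | 3 | 7 | 14 | 0 / 100 / 0% | 0% |
| 2 days | 2-4 | 6-8 | 13-15 | 25 / 50 / 25% | 0% |
| 3 days | 2-4 | 6-8 | 13-15 | 33 / 33 / 33% | 0% |
| 4 days | 1-5 | 5-9 | 12-16 | 38 / 25 / 38% | 25% |
| 5 days | 1-5 | 5-9 | 12-16 | 40 / 20 / 40% | 20% |
| 6 days | 1-6 | 4-10 | 11-17 | 42 / 17 / 42% | 50% |
| 7 days | 1-7 | 4-10 | 11-17 | 43 / 14 / 43% | 57% |

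**Spread of age in the DOL 14 group.** Weekly: √((9 + 4 + 1 + 0 + 1 + 4 + 9)/7) = √4 = 2.0 days. Every 3 days: √(2/3) = 0.82 days.

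**What the spread does if change is gradual.** Assume, for illustration only, a linear change of 2 within-age SDs from DOL 3 to DOL 14. The slope is 2/11 = 0.18 SD per day. The SD of the DOL 14 group is multiplied by √(1 + (slope × age SD)²):
- weekly: √(1 + (0.182 × 2.0)²) = 1.06, an increase of about 6%
- every 3 days: √(1 + (0.182 × 0.82)²) = 1.01, an increase of about 1%

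**The case against.** Much of the case on the other side stands. Tying samples to clinical draws is a deliberate safeguard for very small infants, and the nearest-draw rule is a defined assignment with a soft limit. Infants of at most 1500 g or under 30 weeks, in a NICU in their first two weeks, may well have frequent laboratory tests; with daily draws the problem vanishes. The plan states no primary endpoint or power claim that the blurring would undermine. Data Analysis does not name the ANOVA factor, so a decision to use nominal days is inferred. It remains true that a one-way ANOVA has no place for actual age except as categories.

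A reader might infer three stronger things that the documents do not support:
- **A switch on day 14 that the last sample straddles.** The Background gives a period, the first two weeks, and calls the timing of maturation unknown. An even mix of two levels 2 SDs apart would raise the SD by 41% (√(1 + 2²/4) = 1.41) and halve the apparent shift, but neither the step nor its size is in the protocol.
- **Bias between sick and stable infants.** Nothing in the documents links draw frequency to illness, and Data Analysis plans no such comparison. In the weekly enumeration the mean age is on target at DOL 7 and 14; only the DOL 3 group shifts, by one day.
- **One draw counted as two time points.** The plan calls for three serial samples, so separate draws are the natural reading. What is missing is a rule for a draw that is nearest to two targets.

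**Conclusion.** The concern holds as a minor point. The sampling rule lets a nominal-day value come from another day, and the planned analysis cannot use the true age. The mixing ranges from none (daily draws), through about plus or minus 1 day (every 2 or 3 days), to groups spanning DOL 1-7, 4-10 and 11-17 (weekly). That range rests entirely on an assumed draw frequency and a regular schedule. With gradual change the loss of precision is modest, as the working shows. The reason to act is that age is the longitudinal variable and the remedy costs almost nothing, not that the study's conclusions are shown to be at risk.

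**What to change.** Keep the draws opportunistic, as written. Record the date and time of each preterm draw and of the term heel stick. In Data Analysis, state that NET and NIP results will be analysed with actual postnatal age as the time variable, in a model that allows repeated samples from the same infant (for example, a mixed model with a random infant effect), in place of nominal-day groups. Report the range of actual ages with any nominal-day summary, and let no draw fill two slots.

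An acceptance window alone would not do this: one symmetric about day 14, such as DOL 12-16, still mixes earlier and later samples. Analysis by actual age also keeps every sample.

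The cost is one recorded time per sample, a short addition to Data Analysis and slightly more analysis work. No extra blood or procedure is needed.
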